 - If only Visit 1 or Visit 2 has a score >0, then SAPS-PD will not be repeated in subsequent visits.
- j. The stool sample should be collected during the EoT visit. If subjects discontinue from the study prior to the EoT visit, a stool sample should be collected at the Early Termination visit (as applicable).

AE=adverse event; BDI-II= Beck Depression Inventory II; BM=bowel movement; BP=blood pressure; C-SSRS= Columbia-Suicide

Severity Rating Scale; ECG=electrocardiogram; EoT=end of treatment; FSH=follicle-stimulating hormone; HR=heart rate; L-

Dopa=levodopa; MDS-UPDRS=Movement Disorder Society's Unified Parkinson's Disease Rating Scale; MMSE=Mini-mental State

Examination; PAC-QoL=Patient Assessment of Constipation - Quality of Life;

PAC-SYM=Patient Assessment of Constipation Symptoms; PK=pharmacokinetic(s); RR=respiratory rate; SAPS-PD=Scale for

Assessment of Positive Symptoms – Parkinson's Disease; UPT=urine pregnancy test.

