3.3 Exploratory Objectives and Endpoints

Exploratory objectives of the study are:

- To determine the decrease in efficacy in the blinded placebo withdrawal and washout periods.
- To collect information on the effect of ENT-01 on motor and non-motor symptoms of Parkinson's disease including mood, memory, and hallucinations/delusions.
- To collect information on the effect of ENT-01 on levodopa absorption.
- To collect information on the effect of ENT-01 on the stool microbiome.

Exploratory endpoints include:

- Change from baseline in the weekly CSBM rate during the Placebo Withdrawal and Washout periods.
- Change from baseline in the weekly SBM rate during the Placebo Withdrawal and Washout periods.
- Change from baseline in stool ease of passage during the Placebo Withdrawal and Washout periods.
- Change from baseline in stool consistency during the Placebo Withdrawal and Washout periods.
- Change from baseline in suppository/enema use during Placebo Withdrawal and Washout periods.
- Improvement in frequency and/or severity of hallucinations/delusions during the Fixed Dose period over baseline: Improvement is defined as an improvement of 2.33 points or greater reduction in score from baseline on the SAPS-PD. Up to 40% of subjects are expected to have minor or major hallucinations and/or delusions. The SAPS-PD will be administered at Screening and at Visit 2, and subsequently will only be administered to those subjects with hallucinations and/or delusions on both visits (as determined by a SAPS-PD score >0 at Visit 1 and 2). Subjects with SAPS-PD score >0 at baseline and randomization visits will be included in the analysis.
- Improvement of the symptoms of Parkinson's Disease as assessed by the MDS-MDS-UPDRS: The first 3 parts of the MDS-UPDRS will be administered to determine whether there is any deterioration in overall scores during the treatment period. Motor deterioration will be assessed from Part 3 of the MDS-UPDRS, but total score (Parts 1+2+3) will also be reported. *The assessment will be performed during the “ON” phase, approximately 60 minutes after taking levodopa.* In individuals who are “on” earlier or later, the UPDRS will be performed when they are “ON”.
- Improvement in mood as assessed by the Beck Depression Index (BDI-II): The 21-item BDI-II assesses the intensity of depression. Each item is a list of four statements arranged in increasing severity about a particular symptom of depression.

[figure not shown]

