2.6.3 Exploratory efficacy endpoints

The exploratory efficacy endpoints include:

- A weekly CSBM rate increase of 1 or more compared to baseline and an absolute rate of 3 or more CSBMs per week in the Fixed Dose period (i.e., this is a modification of the Prokinetic Response secondary endpoint using “AND” instead of “OR” as the criterion).
- A weekly SBM rate increase of 1 or more compared to baseline and an absolute rate of 3 or more CSBMs per week in the Fixed Dose period.
- Change from baseline in the weekly CSBM rate during the Placebo Withdrawal and Washout periods.
- Change from baseline in the weekly SBM rate during the Placebo Withdrawal and Washout periods.
- Change from baseline in stool ease of passage during the Placebo Withdrawal and Washout periods.
- Change from baseline in stool consistency during the Placebo Withdrawal and Washout periods.
- Change from baseline in suppository/enema use during Placebo Withdrawal and Washout periods.
- Improvement in frequency and/or severity of hallucinations/delusions during the Fixed Dose period over baseline: Improvement is defined as an improvement of 2.33 points or greater reduction in score from baseline on the Scale for the Assessment of Positive Symptoms -Parkinson's Disease (SAPS-PD). Up to 40% of subjects are expected to have minor or major hallucinations and/or delusions. The SAPS-PD will be administered at Screening, and subsequently will only be administered to those subjects with hallucinations and/or delusions (as determined by an SAPS-PD score >0 at the Screening visit).
- Improvement of the symptoms of Parkinson's Disease as assessed by the UPDRS: The standard four-part UPDRS will be administered to determine whether there is any deterioration in overall scores during the treatment period. Motor deterioration will be assessed from Part 3 of the UPDRS, but total score will also be reported. ***The assessment will be performed during the “ON” phase, approximately 60 minutes after taking levodopa.***
- Improvement in mood as assessed by the Beck Depression Index (BDI-II): The 21-item BDI-II assesses the intensity of depression. Each item is a list of four statements arranged in increasing severity about a particular symptom of depression.

- Improvement in cognition as assessed by the MMSE: The MMSE is an 11-item examination with a score ranging from 0 – 30 with a higher score indicating better memory. The MMSE will be summarized over time.

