4.6.5 Analysis of Exploratory Efficacy Endpoints

Continuous Exploratory Efficacy Endpoints

Continuous endpoints include change from baseline of the following outcomes:

- Weekly CSBM rate during the Placebo Withdrawal and Washout periods
- Weekly SBM rate during the Placebo Withdrawal and Washout periods
- Stool ease of passage during the Placebo Withdrawal and Washout periods
- Stool consistency during the Placebo Withdrawal and Washout periods
- Suppository/enema use during Placebo Withdrawal and Washout periods
- Total score and 3 subdomain scores from PAC-SYM during the Placebo Withdrawal and Washout periods
- Total Score and 4 subdomain scores from PAC-QoL during the Placebo Withdrawal and Washout periods
- Stool microbiome during each study period, defined as the number of species found in the microbiome

- Total sleep time (hours) per day during each study period
- Delay (minutes) in sleep onset per night during each study period
- Total awake time (hours) per night during each study period
- Number of wakes per night during each study period
- Total score from UPDRS and individual part scores to assess the symptoms of Parkinson's Disease during each study period
- Total score from BDI-II to assess the intensity of depression during each study period
- Total score from MMSE to assess cognition during each study period

All continuous exploratory efficacy endpoints will be analyzed in the same manner as the primary efficacy endpoint with treatment, baseline CSBM strata, and corresponding baselines as the independent variables in the ANCOVA model. Changes to the single blind placebo and washout periods will also be repeated using the fixed dose rate or end of fixed dose measurement as baseline. Summary statistics will also be presented by specific fixed dose groups for descriptive purposes only.

Categorical Exploratory Efficacy Endpoints

The following is the lone categorical exploratory efficacy endpoint:

- Improvement in frequency and/or severity of hallucinations/delusions as measured by SAPS-PD score during the Fixed Dose period over baseline for subjects with SAPS-PD score >0 at the Screening visit. Improvement is defined as ≥ 2.33 points reduction in score from baseline on the SAPS-PD

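### The 2.33-point SAPS-PD responder rule cannot be met from a baseline below 2.33, and the SAP's analysis set conflicts with the rule on who is measured

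*SAP*

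**What the plan says.** **Responder definition.** SAP 4.6.5 describes the endpoint as "Improvement in frequency and/or severity of hallucinations/delusions as measured by SAPS-PD score during the Fixed Dose period over baseline" and sets the cut at 2.33 or more "points reduction in score from baseline on the SAPS-PD". Protocol 3.3 uses the same cut: "Improvement is defined as an improvement of 2.33 points or greater reduction in score from baseline on the SAPS-PD". Neither document sets a minimum baseline score.

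**Who is analysed.** SAP 4.6.5 takes the endpoint "for subjects with SAPS-PD score >0 at the Screening visit". Protocol 3.3 says: "Subjects with SAPS-PD score >0 at baseline and randomization visits will be included in the analysis".

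**Who is measured.** Footnote i to the protocol's schedule of events (Table 1, repeated in Appendix 2) says: "If only Visit 1 or Visit 2 has a score >0, then SAPS-PD will not be repeated in subsequent visits". Footnote i to the SAP's own Table 1 carries the same stop rule. SAP 2.6.3, however, makes later administration depend on the Screening score alone: "The SAPS-PD will be administered at Screening, and subsequently will only be administered to those subjects with hallucinations and/or delusions".

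**Baseline and test.** SAP 4.2 takes as baseline the last measurement before the first dose. The schedule includes the SAPS-PD at Visit 2 and dosing starts the next day, so that measurement is Visit 2. The endpoint is compared by Fisher's exact test, with a stratified CMH test if numbers allow. Testing is two-sided at 0.05.

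**The concern.** There are two separate problems.

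The first is a floor. A subject enters with any positive score but must fall by 2.33 points to count. A subject who starts below 2.33 and becomes symptom-free is recorded as not improved. Such subjects are foreseeable, because the expected prevalence of up to 40% explicitly includes minor symptoms. SAP 4.6.5 analyses UPDRS, BDI-II and MMSE as change scores by ANCOVA but gives SAPS-PD only the dichotomy. No planned test would therefore register improvement in mild cases.

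The second is an undefined denominator. The SAP set includes subjects positive at Screening and zero at Visit 2. Under the schedule footnotes they have no later SAPS-PD score. The SAP does not say whether they are dropped, shown as missing or counted as non-responders, so two programmers could produce different tables. SAP section 5 nevertheless states that nothing departs from the protocol-defined analyses.

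**Working it through.** The documents give no sample size, power or expected response rate for this endpoint, so there is no planned figure to reproduce.

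**Step 1: the floor.** Both documents use a score above 0 to mean that symptoms are present, which implies a minimum of 0. The largest possible reduction from baseline *b* is *b* − 0 = *b*. Response needs a reduction of at least 2.33, so it needs *b* ≥ 2.33. Baselines of 1 and 2 allow at most 1 and 2 points and fail; a baseline of 3 can pass. If scores are whole numbers, which the documents do not state, the 2.33 cut acts as a 3-point cut. Requiring a positive score at both visits does not remove the floor.

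**Step 2: the sets side by side.**

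| Visit 1 | Visit 2 | In SAP 4.6.5 set | In Protocol 3.3 set | Measured later, footnote i (both documents) | Measured later, SAP 2.6.3 |
|---|---|---|---|---|---|
| >0 | >0 | yes | yes | yes | yes |
| >0 | 0 | yes | no | no | yes |
| 0 | >0 | no | no | no | no |

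The second row is the conflict, and it lies inside the SAP as well as between the documents. Under SAP 4.2 that subject has a Visit 2 baseline of 0, so could not respond even if measured.

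**Step 3: illustration of size.** Inputs from the documents: up to 40% with symptoms, 80 subjects randomized 1:1 in the second cohort, two-sided 0.05. This gives 0.40 × 80 = 32 subjects, or 16 per arm. Assumed, not in the documents: response of 50% vs 20% among subjects able to respond, and a fraction *f* of symptomatic subjects below 2.33.

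Keeping everyone, the rates become 50%(1 − *f*) and 20%(1 − *f*):
- *f* = 1/3: 33% vs 13%, a difference of 20 points instead of 30.
- *f* = 1/2: 25% vs 10%, a difference of 15 points.

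Power is the sum of the product of the two binomial probabilities over all tables with a Fisher p-value below 0.05.

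| *f* | All 16 per arm | Only those able to respond |
|---|---|---|
| 1/3 | 15% | 17% (11 per arm); 13% (10 per arm) |
| 1/2 | 10% | 12% (8 per arm) |

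At *f* = 1/3 the restricted size is 16 × 2/3 = 10.7, hence both 10 and 11.

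For both cohorts together the numbers are 0.40 × (54 + 40) ≈ 38 active and 0.40 × (18 + 40) ≈ 23 placebo. Power is then 34% keeping and 41% excluding at one third, and 23% and 32% at one half. With a larger assumed effect, 60% vs 20%, and *f* = 1/2, second-cohort power is 17% keeping and 24% excluding.

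**The case against.** The strongest reply is that the consequence is small and conservative. Subjects who cannot respond occur in both randomized arms and pull the difference toward zero, so they cannot create an apparent benefit. The endpoint is exploratory and plays no part in the SAP 4.6.3 success criterion. Excluding these subjects also costs sample size, so second-cohort power barely moves at the 50% vs 20% assumption. All of this stands. It also stands that a fixed threshold deliberately ignores small changes, and that restricting to baselines of at least 2.33 changes the target population. The restricted rate should therefore sit beside the prespecified rate and not replace it.

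A reader might infer three stronger things that the documents do not support:
- *That unmeasured subjects dilute the Fisher test as non-responders.* No rule imputes a missing SAPS-PD score as non-response. The missing-data conventions in SAP 4.2 cover dates, and the zero rule in SAP 4.6.1 covers bowel movements. SAP 4.2 also gives categorical tabulations a category for missing data. Without an imputation rule these subjects would most naturally fall out of the test. The fault is that nothing says so.
- *That the drop from 30 to 20 or 15 points measures lost information.* It leaves out the smaller denominator after exclusion. The power comparison shows a much smaller loss.
- *That the excluded scores are exactly 1 and 2.* This needs whole-number scoring, which is not stated.

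The reply does not remove the floor, and it does not reconcile the sets.

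**Conclusion.** Both parts hold, at low severity. A subject whose baseline is above 0 and below 2.33 cannot be a responder under either document's set. This rests only on a scale minimum of 0. The SAP's Screening-only set and administration rule contradict Protocol 3.3, the protocol's stop rule and the SAP's own footnote i, and the handling of the affected subjects is undefined.

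The size cannot be determined, because the documents give no SAPS-PD score distribution; if few subjects fall below 2.33 the effect nearly disappears. Under the assumed 50% vs 20%, excluding those below threshold changes second-cohort power by about 2 points (15% to 17%, or 10% to 12%), and at 10 per arm not even favourably. For both cohorts the gain is 7 to 9 points. The responder test is weak with or without the restriction. The case for change is therefore interpretability and a defined denominator more than power. The primary result is untouched.

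**What to change.** In SAP 4.6.5 and 2.6.3:
1. Define the set as in Protocol 3.3, positive at both Visit 1 and Visit 2. Name Visit 2 as baseline, consistent with SAP 4.2, and state how a missing Fixed Dose score is handled.
2. Add SAPS-PD change from baseline to the continuous exploratory endpoints in 4.6.5, using the ANCOVA already specified there: treatment, baseline CSBM stratum and baseline SAPS-PD score. Improvement in mild cases then counts.
3. Report the 2.33-point responder rate in subjects with a baseline of at least 2.33, alongside the prespecified rate in all symptomatic subjects.

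This needs only SAP wording and data already scheduled for collection. The costs are a smaller denominator for the restricted responder rate and one more exploratory analysis.

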4.7. Pharmacokinetic Analysis

The plasma concentration data and PK parameters of L-Dopa will be summarized based on the PK population by time point (pre-dose, 20, 40 and 60 minutes post-dose) and dose level. These measures will be presented in listings as well.

An increase of $>30\%$ in peak plasma level of L-Dopa during treatment from baseline would indicate clinically significant increase in absorption attributable to ENT-01. The frequency and percentage of subject with clinically significant increase will be tabulated without formal statistical analysis for the PK population.

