d. Sites will use a centralized computer-based system (IWRS) to obtain the randomization bottle(s) assigned to each subject.

- Subjects with baseline CSBMs from 0 to 0.9 will be randomized to begin treatment with ENT-01 150 mg or 6 tablets of placebo.
- Subjects with baseline CSBMs from 1.0 to 3.0 will be randomized to begin treatment with ENT-01 75 mg or 3 tablets of placebo.
- Subjects will self-administer study medication at home. The dose will be taken upon awakening, on an empty stomach with 8 oz. of water and no solid food will be taken for another 60 minutes. Subjects will remain in a sitting upright or standing position for at least 60 minutes after taking medication.
- Subjects will be advised to stay at home for 4 to 6 hours after taking the first dose of medication in case there is a need to evacuate urgently. After the first dose, subjects will know if and when to leave the house.

e. A subset of 20 subjects from this study population will participate in an L-Dopa PK Study, as follows:

- Visits 2 and 6: Blood draws for L-dopa levels (PK) will be drawn at Time zero.
- The first daily dose of L-Dopa will be administered on site after the first blood draw. There will be another blood draw at 20, 40, and 60 minutes post- L-Dopa dose.
- Visits 3, 4, and 5: Immediately upon arrival at the study site, the subject will take study medication (ENT-01 or placebo) on an empty stomach. Blood will be drawn at Time zero. 30 to 60 minutes after taking ENT-01 or placebo, the subject will take their first daily dose of L-Dopa. Blood will be drawn again 20, 40, and 60 minutes post-L-Dopa dose. The subject may have food 60 minutes after taking ENT-01.

f. Rescue medications will be dispensed as needed and instructions given concerning laxatives and other medications to treat constipation.

g. Subjects will be educated concerning use of the electronic diary to report stools immediately after a bowel movement.

CONFIDENTIAL

19April21_7.0

- h. The first 3 parts of the MDS-UPDRS should be administered while the subject is in an ON state, approximately one hour after taking L-Dopa (if applicable). In some cases, subjects will reach the "on" state earlier or later than at 60 minutes. In those cases, MDS-UPDRS should be performed when the Subject is "on".
- i. Those subjects who have a SAPS-PD score >0 on Visits 1 and 2 will have the SAPS-PD and hallucination/delusion questionnaire at all subsequent visits.

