- Improvement in cognition as assessed by the MMSE: The MMSE is an 11-item examination with a score ranging from 0 – 30 with a higher score indicating better memory. The MMSE will be summarized over time.
- Change in plasma L-Dopa levels 20, 40, and 60 minutes after L-Dopa and ENT-01 dose: An increase of >30% in peak plasma level during treatment versus baseline would indicate clinically significant increase in absorption attributable to ENT-01 (20 subjects).
- Change in stool microbiome during treatment: Since ENT-01 has antimicrobial properties in vitro, it may alter the intestinal microbiome; the subject's stool will be analyzed for common intestinal bacteria and viruses at Baseline and Fixed Dose, periods (20 subjects). If subjects discontinue from the study prior to the end of the Fixed Dose period, stool will be collected and analyzed at the Early Termination visit, as applicable.

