b. Three sets will be taken. Time points to be defined. Orthostatic vital signs will include supine BP and HR, sitting or standing BP and HR, RR, and body temperature. Supine measurements will be taken after the subject has been in the supine position for at least 5 minutes. Sitting or standing measurements will be taken within 5 minutes of sitting or standing from the supine position. Respiration rate and body temperature will be taken after the subject has been sitting or standing for at least 5 minutes.

c. For women of child-bearing potential, on-site with urine pregnancy test kit. If the on-site UPT is positive, a serum pregnancy test will be done. For post-menopausal women <60 years or of age, a serum FSH will be done at the screening visit only.

d. Sites will use a centralized computer-based system to obtain the randomization bottle(s) assigned to each subject.

- Subjects with baseline CSBMs from 0 to 0.9 will be randomized to begin treatment with ENT-01 150 mg or 6 tablets of placebo.
- Subjects with baseline CSBMs from 1.0 to 3.0 will be randomized to begin treatment with ENT-01 75 mg or 3 tablets of placebo.
- Subjects will self-administer study medication at home. The dose will be taken upon awakening, on an empty stomach with 8 oz. of water.
- Subjects will be advised to stay at home for 4 to 6 hours after taking the first dose of medication in case there is a need to evacuate urgently. After the first dose, subjects will know if and when to leave the house.

- e. A subset of 20 subjects from this study population will participate in an L-Dopa PK Study, as follows:
 - Visits 2 and 6: Blood draws for L-dopa levels (PK) will be drawn at Time zero.
 - The first daily dose of L-Dopa will be administered on site after the first blood draw. There will be another blood draw at 20, 40, and 60 minutes post- L-Dopa dose
 - Visits 3, 4, and 5: Immediately upon arrival at the study site, the subject will take study medication (ENT-01 or placebo) on an empty stomach. Blood will be drawn at Time zero. 30 to 60 minutes after taking ENT-01 or placebo, the subject will take their first daily dose of L-Dopa. Blood will be drawn again 20, 40, and 60 minutes post-L-Dopa dose. The subject may have food 60 minutes after taking ENT-01.
- f. Rescue medications will be dispensed as needed and instructions given concerning laxatives and other medications to treat constipation.

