3. SUBJECT POPULATIONS

3.1. Population Definitions

The following subject populations will be evaluated and used for presentation and analysis of the data:

- **Safety Population:** The Safety Population will consist of all subjects who receive at least one dose of study medication during the study. Subjects will be analyzed based on the treatment that they actually received. All safety analyses will be based on this population.
- **Modified ITT Population:** The modified Intent-to-Treat (mITT) Population will include subjects who are randomized and have the stool diary assessments both at baseline and at least one post baseline time-point. Subjects who are found later to have inclusion/exclusion violations will be excluded from the mITT population.
- **Fixed Dose Population:** The Fixed Dose Population will include all subjects who are in mITT Population who enter the Fixed Dose period of the study and are in the treatment period for at least seven days, not including the date of randomization.
- **Efficacy Evaluable Population:** The Efficacy Evaluable Population will include subjects who are in the Fixed Dose Population, complete the Fixed Dose period, are compliant with study medication in the Fixed Dose period, and have no major protocol deviations.
- **Pharmacokinetics Population:** Pharmacokinetics Population will include subjects with a least one L-Dopa PK result.

The precise reasons for excluding subjects from the Efficacy Evaluable Population will be fully defined and documented prior to the unblinded interim analysis.

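### The plan credits a rise of more than 30% in a subject's peak L-Dopa to ENT-01, although the PK population includes placebo subjects and SAP 4.7 specifies no comparison by arm

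*SAP*

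**What the plan says.** Protocol 3.3 sets the threshold: "An increase of >30% in peak plasma level during treatment versus baseline would" show a clinically significant increase due to ENT-01. SAP 2.6.3 repeats this. SAP 4.7 states it again, saying that such a rise would "indicate clinically significant increase in absorption attributable to ENT-01", and adds that the number and percentage of subjects who meet it will be "tabulated without formal statistical analysis for the PK population".

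For concentrations and PK parameters, SAP 4.7 gives the grouping as time point and dose level: "pre-dose, 20, 40 and 60 minutes post-dose) and dose level". It does not name randomized arm for these summaries or for the table of flagged subjects.

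The population is defined in SAP 3.1: "Pharmacokinetics Population will include subjects with a least one L-Dopa PK result". It is not limited to ENT-01. In SAP 2.4, Table 1 footnote e, the dosing at Visits 3, 4 and 5 reads: "the subject will take study medication (ENT-01 or placebo) on an empty stomach". L-Dopa follows 30 to 60 minutes later. At Visit 2 (baseline) and Visit 6, footnote e describes L-Dopa with no preceding study tablets.

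On size, protocol Table 1 footnote e says: "A subset of 20 subjects from this study population will participate in an L-Dopa PK Study". Protocol 3.3 and the SAP's own footnote e also say 20, but SAP 2.6.3 says 10. SAP 2.6.4 announces a separate SAP for the PK analysis, which is not among the documents.

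**The concern.** A change within one subject from one baseline visit cannot show by itself that ENT-01 caused it. At least three things other than a drug effect can move it:

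- Peak L-Dopa varies from visit to visit.
- The peak is read as the highest of a few draws, the last at 60 minutes, so the true peak may be missed. This adds noise.
- L-Dopa follows study tablets at the on-treatment visits but not at baseline, so any effect of the dosing procedure enters the change. The placebo arm, dosed by the same procedure, is the concurrent control for this.

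The gap stands out within the SAP. Section 4.6.5 gives the other exploratory endpoints an ANCOVA with treatment as a factor, or Fisher's exact test against placebo. Section 4.8 has no formal testing either, but summarises safety data by treatment group.

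At stake is the exploratory objective on levodopa absorption. As written, ordinary variation could be reported as an effect of ENT-01 on a medicine that many of these patients take every day.

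**Working it through.** The plan states no error rate, power or precision for this rule, so there is no figure of its own to reproduce.

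**Step 1: who can be flagged.** SAP 3.1 admits anyone with an L-Dopa result, and footnote e doses sub-study subjects with ENT-01 or placebo. The rule in SAP 4.7 does not refer to arm. A placebo subject whose peak rises by more than 30% therefore meets a criterion worded as attributable to ENT-01. This needs no assumption about variability.

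**Step 2: how often chance alone flags a subject.** The documents give the threshold (more than 30%). They give no within-subject CV for peak L-Dopa, and they do not say which visit or visits count as on treatment. Both are assumptions here.

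Assume no drug effect and a log-normal peak with within-subject standard deviation σ = √ln(1 + CV²) on the log scale. For one on-treatment visit against one baseline visit:

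P(flag) = 1 − Φ( ln 1.3 / (σ√2) ), with ln 1.3 = 0.2624.

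- CV 20%: σ = √ln 1.04 = 0.198 and σ√2 = 0.280, so P = 1 − Φ(0.937) = 17.4%.
- CV 30%: σ = √ln 1.09 = 0.294 and σ√2 = 0.415, so P = 1 − Φ(0.632) = 26.4%.

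If a rise at either Visit 3 or Visit 4 is enough, the two ratios share a baseline. The probability was simulated with 1,000,000 subjects.

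| Assumed CV | One visit | Either Visit 3 or Visit 4 |
|---|---|---|
| 10% | 3% | 6% |
| 15% | 11% | 18% |
| 20% | 17% | 28% |
| 30% | 26% | 40% |
| 40% | 32% | 46% |
| 50% | 35% | 50% |

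A chance rate of 25% needs a CV of about 28% for one visit, or about 18% for either of two.

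**Step 3: what this means in subjects.** At CV 30% and one visit, the expected number flagged with no drug effect is 20 × 0.264 = 5.3 of 20, or 10 × 0.264 = 2.6 of 10. The chance of at least one flag among 10 is 1 − 0.736¹⁰ = 95%. At CV 10% the expected numbers fall to 0.6 of 20 and 0.3 of 10.

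**Step 4: what a comparison by arm could show.** For the ENT-01/placebo ratio of change in peak at one visit, with n per arm, the 95% CI is the estimate multiplied and divided by exp(1.96 × σ√2 × √(2/n)). At CV 30%:

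- 10 per arm: exp(1.96 × 0.415 × √0.2) = 1.44
- 5 per arm: exp(1.96 × 0.415 × √0.4) = 1.67

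A t quantile would widen these somewhat. With an estimated ratio of 1.0, either interval would still contain a 30% rise.

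**The case against.** The endpoint is exploratory, the objective is only to collect information, and SAP 4.7 disclaims formal analysis. This stands and limits the importance of the point. But a descriptive table supports descriptive wording; it does not support a statement of cause.

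A reader might infer that the trial has no placebo comparison of L-Dopa at all. The documents do not support that. The separate PK SAP announced in SAP 2.6.4 may contain one, and dose level in SAP 4.7 might include placebo as a level. What can be said is that SAP 4.7 specifies none. That phrase also governs the concentration and parameter summaries, not the table of flagged subjects.

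A reader might also infer that chance would label a quarter or more of subjects as affected. That does not follow either. It needs a CV that the documents do not give, and the either-visit figures rest on a flagging rule that they do not state.

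All sub-study subjects are sampled at Visit 5 after placebo tablets and at Visit 6 off study drug, so some visit-to-visit variation will be visible within subjects. This helps interpretation, but the attribution rule does not use those visits.

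Finally, a comparison by arm will be imprecise. Protocol 4.1 takes the first twenty consenting subjects, with no stated stratification of the sub-study by arm, so 10 against 10 is not guaranteed. This is true, but an interval shows the imprecision and a bare percentage hides it.

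**Conclusion.** The point holds as a fault in a stated rule, repeated in three places. A within-subject rise is attributed to ENT-01 whatever tablets the subject took, and SAP 4.7 sets no comparison by arm against which to judge it.

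The share flagged by chance is conditional. Over assumed CVs of 10% to 50%, with a log-normal peak and no drug effect, it is about 3% to 35% at one visit and about 6% to 50% if either Visit 3 or Visit 4 counts. The fault in the rule does not depend on where the true CV lies.

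The point is minor for the trial as a whole. It affects the answer on levodopa absorption and leaves the primary efficacy conclusion untouched.

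**What to change.** - In SAP 4.7, tabulate the flag of more than 30% by randomized arm, and state which visit or visits define it.
- Report the ENT-01/placebo ratio of baseline-adjusted change in log peak with a 95% CI, labelled as a descriptive estimate.
- In SAP 4.7, SAP 2.6.3 and protocol 3.3, replace the attribution to ENT-01 with neutral wording, such as a rise from baseline of more than 30%.
- Reconcile the sub-study size: 20 in protocol 3.3 and in footnote e of both documents, 10 in SAP 2.6.3.
- Carry the same rule into the separate PK SAP, so that the two plans agree.

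The cost is one table, one model and a few sentences, with no new data. The protocol wording has to go through an amendment under protocol 11.7. With 10 to 20 subjects the interval will be wide, and the report should say so.
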